6.1.1 Induction Therapy: Week 0 to Week 12 (Last Dose at Week 10)

Double-blind Induction Therapy is separated into Part A for administration of multiple ascending IV doses of KHK4083 (or placebo) to subjects in Cohorts 1 - 3 and Part B for administration of the recommended IV dose (one of three dose levels identified in Part A) of KHK4083 (or placebo) to subjects in Cohort 4. Subjects in Part A are prohibited from participating in Part B.

Subjects in each cohort will be randomly assigned in a 3:1 ratio to receive KHK4083 or placebo by IV infusion over 60 minutes (\pm 10 minutes). Each subject will receive a total of 6 treatments (one IV infusion per treatment) every 2 weeks from Week 0 (Day 1) to Week 10 of Induction Therapy. Safety assessments (e.g., after 2 treatments for 1.0 mg/kg and 3 treatments for 3.0 and 10 mg/kg are administered and 14-day safety data from the last treatment are available) will determine whether dosing will continue for subjects within a cohort and if the investigational product will be administered at the next higher dose level for subjects in the next cohort in Part A or for Cohort 4 in Part B (refer to Section 6.3 for details on the Safety Monitoring Plan).

For subjects in all cohorts, a sigmoidoscopy with biopsy is scheduled at Week 12 to assess improvement in the mucosa from Baseline (Week 0) to Week 12. It is highly recommended that the sigmoidoscopy with biopsy be performed within 7 to 13 days prior to the Week 12 visit. The sigmoidoscopy results from the central reader are required before a subject receives treatment in the OLE/LTE Therapy phase.

6.1.2 Long-term Extension Therapy: Week 12 (First Dose) to Week 52

The LTE is only active for subjects who entered it prior to approval of Amendment 2. Subjects who sign an ICF under Amendment 2 are eligible for the OLE (see Section 6.1.3).

Subjects who completed double-blind Induction Therapy (i.e., at least five of six treatments) and had a clinical response or mucosal healing were eligible to continue in double-blind LTE Therapy. A clinical response is defined as a reduction in the total Mayo Clinic score of at least 3 points and a decrease of at least 30% from Baseline (Week 0) to Week 12, and a reduction in the rectal bleeding subscale of at least 1 point from Baseline (Week 0) to Week 12 or an absolute rectal bleeding score of 0 or 1 at Week 12. Mucosal healing is defined as a mMES of 0 or 1.

All subjects who qualified were to have been given two options:

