For subjects in all cohorts, a sigmoidoscopy with biopsy will be performed at Week 12 to assess improvement in the mucosa based on a mean change in the mMES from Baseline (Week 0) to Week 12. It is highly recommended that the sigmoidoscopy with biopsy be performed within 7 to 13 days prior to the Week 12 visit.

8.1.4.2 Open-label/Long-term Extension Maintenance Therapy: Week 12 (First Dose) to Week 52

All subjects who qualify and continue double-blind LTE or start open-label maintenance therapy will be administered one KHK4083 or placebo (LTE) or one KHK4083 (OLE) IV infusion at Weeks 12, 16, 20, 24, 28, 32, 36, 40, 44, and 48 for a total of 10 additional treatments followed by an End-of-OLE/LTE Therapy visit at Week 52, and then proceed to the OLE/LTE Therapy Follow-up Period (Week 56 through Week 64). The treatment at Week 12 will be administered at the scheduled visit or within 7 days after Week 12. The OLE dose will be the same as the dose for that cohort during the induction therapy, unless dose-reduction is recommended by the Safety Monitoring Committee and Sponsor (see Section 6.3).

During OLE/LTE Therapy, corticosteroid (glucocorticoid) dosages of prednisolone or its equivalent will be permitted to be tapered (decreasing by up to 2.5 mg/day per week) and other concomitant medications for UC may be tapered. Bolus or “rescue” treatment with systemic corticosteroids or topical corticosteroid enemas or suppositories (in addition to the dose of oral corticosteroids at Screening) is permitted only after Week 12 evaluations are

complete. A sigmoidoscopy with biopsy will be performed at the End-of-OLE/LTE Therapy visit at Week 52 or within 21 days prior to Week 52.

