8.1.5 Post-treatment Follow-up Period

Post-treatment Follow-up assessments will continue for 16 weeks after the last infusion associated with the subject's treatment period. For subjects who only receive Induction Therapy (i.e., last dose at Week 10 and do not continue in OLE/LTE Therapy), the Post-treatment Follow-up visits will be at Weeks 16, 20, and 26. For all subjects who receive both Induction Therapy and OLE/LTE Therapy (last dose at Week 48), the Post-treatment Follow-up visits will be at Weeks 56, 60, and 64. Subjects removed from the study for AEs will be followed until there is a return to the subject's baseline condition, or until a clinically satisfactory resolution is achieved. The date of the subject's last post-treatment study visit will be considered the End-of-Study date.

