4.1 General

General descriptive statistics for continuous variables include the n (number of observed values), the mean, standard deviation, median, minimum, and maximum values. For categorical variables, the number and percentage of subjects with a specific level of the variable will be presented. The percentage will be calculated using the subjects with a reported value. Counts of missing subjects will be identified for variables that had one or more subjects with a missing result. Descriptive statistics will be presented by treatment Cohort (KHK4083 dose levels; combined KHK4083; and placebo) and by visit.

Unless there are any notes, the following rules will be applied for all tables and figures;

- Data from placebo subjects in each Cohort will be combined, not depending on treatment period (Double-Blind Induction Therapy, Long-Term Extension Therapy, Open-Label Extension Therapy, or Follow-up).
- In the case that Screening or Baseline is necessary in the tables and figures related to LTE Therapy Period, OLE Therapy Period, or Follow-up Period, the data at Screening or Baseline will be used or displayed.
- Double-Blind Therapy Period will be defined as the period including both Double-Blind Induction Therapy Period and LTE Therapy Period.
- When “Week xx” (xx: number) is necessary, “Week xx” displayed on CRF will be used or displayed.

To explain how data are summarized, the figure showing the relationship between period and dose of Investigational Product is displayed in Figure 3 and the table defining the category is displayed in Table 2.

[figure not shown]
	Forms			
	Title	Statistical Analysis Plan Template		
	Code	Version	Effective Date	Page
	FRM_ST03_032	01	23 Apr 2015	20 of 53

Figure 3 Relationship between Period and Dose of Investigational Product

Subjects who do not move to OLE/LTE Therapy

Subjects who move to OLE/LTE Therapy

[figure not shown]

Table 2 Category in Tables and Figures

	4083 Randomized				Placebo Randomized			
	Cohort 1	Cohort 2	Cohort 3	Cohort 4	Cohort 1	Cohort 2	Cohort 3	Cohort 4
Summary Pattern	Category In Tables and Figures							
Double-Blind Induction Therapy Period	1.0 mg/kg	3.0 mg/kg	10 mg/kg	1.0, 3.0 or 10 mg/kg	Placebo			
Double-Blind Therapy Period ¹⁾								
Double-Blind Therapy Period and Double-Blind Therapy Follow-up Period ²⁾								
LTE Therapy Period								
LTE Therapy Period and Double-Blind Therapy Follow-up Period	1.0 mg/kg	3.0 mg/kg	10 mg/kg	1.0, 3.0 or 10 mg/kg	Placebo ³⁾			

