OLE Therapy Period								
OLE Therapy Period and OLE Therapy Follow-up Period								

1) Double-Blind Therapy Period includes both Double-Blind Induction Therapy Period and LTE Therapy Period.

2) Double-Blind Therapy Follow-up Period includes both Follow-up Periods after Double-Blind Therapy Period and LTE Therapy Period.

3) For subjects randomized to Placebo, they receive 4083 administration during the duration but they are summarized as one category as "Placebo".

Image which shows the relationship between summary pattern and data will be displayed in Figure 4.

Figure 4 Summary Patterns

Forms

Title Statistical Analysis Plan Template

Code

Version

Effective Date

[figure not shown]
Page

FRM_ST03_032

01

23 Apr 2015

21 of 53

General reporting conventions will include the following:

- The baseline value for any measurement is the last value obtained prior to receiving administration of KHK4083 or placebo on Day 1 at Week 0. All nominal time points will be used for analysis; actual assessment times will not be used to reclassify the time point at which a measure was taken.

	Forms			
	Title	Statistical Analysis Plan Template		
	Code	Version	Effective Date	Page
	FRM_ST03_032	01	23 Apr 2015	22 of 53

- Study day: Study day will be calculated relative to the date of KHK4083 or placebo administration (Day 1) as:
 - (If Date of event \geq Date of first investigational product administration) Date of event – Date of first investigational product administration + 1 and
 - (If Date of event $<$ Date of first investigational product administration) Date of event – Date of first investigational product administration

This formula will be used when calculating days to a specific event (i.e., concomitant medication and/or AE start date). A negative study day indicates an event prior to investigational product administration.

- Unless otherwise noted, all percentages will be presented to one decimal place.
- Individual data listings of all data represented on the eCRF will be provided as an appendix to facilitate investigation of the tabulated values and to allow for the clinical review of all variables. All data listings will be sorted by dose Cohort, site-subject number, visit, and time points where appropriate.
- Post-dose data from unscheduled visits will be excluded from the summary tables but included in the data listings.

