 - Change from baseline in corticosteroid (glucocorticoid) dosages at Week 16 through LTE Therapy Follow-up Period = Glucocorticoid dosages at Week 16 through LTE Therapy Follow-up Period - Baseline glucocorticoid dosages
 - Change from baseline in corticosteroid (glucocorticoid) dosages at Week 16 through OLE Therapy Follow-up Period = Glucocorticoid dosages at Week 16 through OLE Therapy Follow-up Period - Baseline glucocorticoid dosages
- Duration of glucocorticoid-free treatment will be defined as the duration that no glucocorticoid listed in Section 9.3 is used from Week 16 through Follow-up 3.
 - Duration of glucocorticoid-free treatment (days) = Date of first glucocorticoid after Week 16 visit - Date of Week 16 visit
 - If the subject received glucocorticoid on the date of Week 16 visit, the duration of glucocorticoid-free treatment for the subject is 0.

A comparison between treatments (each KHK4083 dose level versus placebo) will be performed using an ANCOVA model with changes from Baseline in UCEIS, total Mayo Clinic score and partial Mayo Clinic score at Week 52 during Double-Blind Therapy Period as dependent variables, treatment as fixed effect and baseline value as covariate. The number of subjects and the number of subjects considered in the model will be provided by treatment. The adjusted means for treatments (least squares means) and the relative 95% CIs will be presented. The difference between the adjusted means for each treatment groups from placebo (Difference in Least Squares Mean from Placebo) will be calculated with the relative 95% CI and p-value. If ANCOVA cannot be applied

	Forms			
	Title	Statistical Analysis Plan Template		
	Code	Version	Effective Date	Page
	FRM_ST03_032	01	23 Apr 2015	33 of 53

due to the issue that the parameters cannot be estimated appropriately, these analyses using ANCOVA for Week 52 will not be applied.

Means with SDs for the efficacy variables (mMES, UCEIS, total Mayo score and partial Mayo score) at all visits will be performed graphically by each treatment (e.g. Placebo, 1.0 mg/kg, 3.0 mg/kg, or 10 mg/kg) and by Double-Blind Therapy Period and OLE Therapy Period. For partial Mayo score, Means with SDs as all visits will be performed graphically by “Double-Blind Therapy Period and Double-Blind Therapy Follow-up Period” and “OLE Therapy Period and OLE Therapy Follow-up Period”. Mean changes from Baseline will also be performed in the same manner.

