Table 14.2-3.2.1	Summary of Score and Change from Baseline in UCEIS During Long-Term Extension Therapy Period / Full Analysis Set
Table 14.2-3.2.2	Summary of Score and Change from Baseline in UCEIS During Open-Label Extension Therapy Period / Full Analysis Set
Table 14.2-3.3.1	Summary of Score and Change from Baseline in Total Mayo Score During Long-Term Extension Period / Full Analysis Set
Table 14.2-3.3.2	Summary of Score and Change from Baseline in Total Mayo Score During Open-Label Extension Period / Full Analysis Set
Table 14.2-3.3.3	Summary of Score and Change from Baseline in Partial Mayo Clinic Scores During Long-Term Extension Therapy Period and Double-Blind Therapy Follow-Up Period / Full Analysis Set
Table 14.2-3.3.4	Summary of Score and Change from Baseline in Partial Mayo Clinic Scores During Open-Label Extension Therapy Period and Open-Label Extension Therapy Follow-Up Period / Full Analysis Set
Table 14.2-3.4.1	Summary Score and Change from Baseline in IBDQ Total Score During Long-Term Extension Therapy Period and Double-Blind Therapy Follow-Up Period / Full Analysis Set
Table 14.2-3.4.2	Summary Score and Change from Baseline in IBDQ Total Score During Open-Label Extension Therapy Period and Open-Label Extension Therapy Follow-Up Period / Full Analysis Set
Table 14.2-3.4.3	Summary Score and Change from Baseline in IBDQ - Bowel-Related Symptoms Score During Long-Term Extension Therapy Period and Double-Blind Therapy Follow-Up Period / Full Analysis Set
Table 14.2-3.4.4	Summary Score and Change from Baseline in IBDQ - Bowel-Related Symptoms Score During Open-Label Extension Therapy Period and Open-Label Extension Therapy Follow-Up Period / Full Analysis Set
Table 14.2-3.4.5	Summary Score and Change from Baseline in IBDQ - Systemic Function Score During Long-Term Extension Therapy Period and Double-Blind Therapy Follow-Up Period / Full Analysis Set
Table 14.2-3.4.6	Summary Score and Change from Baseline in IBDQ - Systemic Function Score During Open-Label Extension Therapy Period and Open-Label Extension Therapy Follow-Up Period / Full Analysis Set
Table 14.2-3.4.7	Summary Score and Change from Baseline in IBDQ - Social Function Score During Long-Term Extension Therapy Period and Double-Blind Therapy Follow-Up Period / Full Analysis Set
Table 14.2-3.4.8	Summary Score and Change from Baseline in IBDQ - Social Function Score During Open-Label Extension Therapy Period and Open-Label Extension Therapy Follow-Up Period / Full Analysis Set

Forms

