9.5 Figures

Number	Title
Figure 15.1.1	Least Squares Means Adjusted for Baseline of MMES at Week 12 / Full Analysis Set
Figure 15.1.2	Difference in Least Squares Means from Placebo Adjusted for Baseline of MMES at Week 12 / Full Analysis Set
Figure 15.2.1	Least Squares Means of UCEIS at Week 12 / Full Analysis Set
Figure 15.2.2	Difference in Least Squares Means from Placebo of UCEIS at Week 12 / Full Analysis Set
Figure 15.2.3	Least Squares Means of Total Mayo Clinic Scores at Week 12 / Full Analysis Set
Figure 15.2.4	Difference in Least Squares Means from Placebo of Total Mayo Clinic Scores at Week 12 / Full Analysis Set
Figure 15.2.5	Least Squares Means of Partial Mayo Clinic Scores at Week 12 / Full Analysis Set
Figure 15.2.6	Difference in Least Squares Means from Placebo of Partial Mayo Clinic Scores at Week 12 / Full Analysis Set
Figure 15.3.1	MMES During Double-Blind Therapy Period / Full Analysis Set
Figure 15.3.2	MMES During Open-Label Extension Therapy Period / Full Analysis Set

Forms

Title Statistical Analysis Plan Template

Code

Version

Effective Date

Page

FRM_ST03_032

01

23 Apr 2015

49 of 53

Number	Title
Figure 15.3.3	UCEIS During Double-Blind Therapy Period / Full Analysis Set
Figure 15.3.4	UCEIS During Open-Label Extension Therapy Period / Full Analysis Set
Figure 15.3.5	Total Mayo Clinic Scores During Double-Blind Therapy Period / Full Analysis Set
Figure 15.3.6	Total Mayo Clinic Scores During Open-Label Extension Therapy Period / Full Analysis Set
Figure 15.3.7	Partial Mayo Clinic Scores During Double-Blind Therapy Period and Double-Blind Therapy Follow-Up Period / Full Analysis Set
Figure 15.3.8	Partial Mayo Clinic Scores During Open-Label Extension Therapy Period and Open-Label Extension Therapy Follow-Up Period / Full Analysis Set
Figure 15.3.9	Change from Baseline of MMES During Double-Blind Therapy Period / Full Analysis Set
Figure 15.3.10	Change from Baseline of MMES During Open-Label Extension Therapy Period / Full Analysis Set
Figure 15.3.11	Change from Baseline of UCEIS During Double-Blind Therapy Period / Full Analysis Set
Figure 15.3.12	Change from Baseline of UCEIS During Open-Label Extension Therapy Period / Full Analysis Set
Figure 15.3.13	Change from Baseline of Total Mayo Clinic Scores During Double-Blind Therapy Period / Full Analysis Set
Figure 15.3.14	Change from Baseline of Total Mayo Clinic During Open-Label Extension Therapy Period / Full Analysis Set

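### The double-blind summaries after Week 12 combine induction-only follow-up with the LTE track, so a dose group's mean can move only because different subjects are measured

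*SAP*

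**What the plan says.** **Periods (SAP 4.1).** "Double-Blind Therapy Period will be defined as the period including both Double-Blind Induction Therapy Period and LTE Therapy Period". Footnote 2 to Table 2 then adds the follow-up: "Double-Blind Therapy Follow-up Period includes both Follow-up Periods after Double-Blind Therapy Period and LTE Therapy Period". Since LTE already lies inside the double-blind period, the footnote only makes sense if its two follow-ups are the one after induction and the one after LTE. The column categories in Table 2 are dose level and placebo. LTE entry is not a category.

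**Outputs.** SAP 7.3 states: "For partial Mayo score, Means with SDs as all visits will be performed graphically by" the therapy period combined with its follow-up. Figure 15.3.7 in SAP 9.5 is titled "Partial Mayo Clinic Scores During Double-Blind Therapy Period and Double-Blind Therapy Follow-Up Period / Full Analysis Set", and Figure 15.3.15 is the change-from-baseline version. Table 14.2-3.3.3 in SAP 9.4 is "Summary of Score and Change from Baseline in Partial Mayo Clinic Scores During Long-Term Extension Therapy Period and Double-Blind Therapy Follow-Up Period". For the IBDQ, SAP 7.3 expressly lists the induction follow-up weeks together with Weeks 2 to 52. SAP 4.4 presents available data at each time point.

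**Who is on each track.** Under Protocol 6.1.2, subjects who completed induction and "had a clinical response or mucosal healing were eligible to continue in double-blind LTE Therapy". Those who did not qualify received no more study treatment and went into the induction follow-up.

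**Visits.** For subjects receiving induction only, last dosed at Week 10, Protocol 8.1.5 says "the Post-treatment Follow-up visits will be at Weeks 16, 20, and 26". In LTE, Protocol 8.1.4.2 schedules an "IV infusion at Weeks 12, 16, 20, 24, 28, 32, 36, 40, 44, and 48", then a visit at Week 52 and follow-up at Weeks 56, 60 and 64.

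**The concern.** A reader takes a mean plotted by visit for one dose group as the course of one set of subjects. Here the set changes. One track was selected on its Week 12 outcome and continues its assigned infusions (drug or placebo). The other is no longer dosed and, under Protocol 8.5.1, may receive treatments that are otherwise prohibited. The two tracks are seen at partly different weeks.

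What is at stake is the reading of the exploratory trends after Week 12, mainly partial Mayo and IBDQ. A drop at one visit and a rise at the next could be taken for a gain or loss of effect when no subject has changed.

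**Working it through.** The plan gives no figure for this point, so there is none to reproduce. The check is a visit map and a constant-score calculation.

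**1. Who is measured, on protocol week labels**

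| Visit | LTE track | Induction-only track |
|---|---|---|
| Week 12 | yes | yes |
| Weeks 16, 20 | yes | yes |
| Week 24 | yes | no |
| Week 26 | no | yes |
| Weeks 28 to 52 | yes | no |
| Weeks 56, 60, 64 | yes | no |

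**2. Formula.** Let n_L subjects with mean a be in LTE and n_F with mean b be in induction-only follow-up, and hold every score constant after Week 12.

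- Weeks 16 and 20: (n_L·a + n_F·b)/(n_L + n_F)
- Week 24 and Weeks 28 to 52: a
- Week 26: b
- Step from Week 20 to 24: −(b − a)·n_F/(n_L + n_F)
- Step from Week 24 to 26: b − a
- Step from Week 26 to 28: −(b − a)

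**3. Illustration.** A Part A dose group has 9 active subjects (Protocol 12.3.4). The rest is assumed: 4 in LTE with mean partial Mayo 2 and 5 in induction-only follow-up with mean 5.

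- Weeks 12, 16 and 20: (4·2 + 5·5)/9 = 33/9 = 3.67
- Week 24: 2.00 (step −1.67)
- Week 26: 5.00 (step +3.00)
- Weeks 28 to 52: 2.00 (step −3.00)

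With 2 to 6 of the 9 in LTE and a gap of 1 to 4 points, the step from Week 20 to 24 runs from −(3/9)·1 = −0.33 to −(7/9)·4 = −3.11. The step from Week 24 to 26 runs from +1 to +4, which is the assumed gap itself.

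**4. Recommended-dose group.** This has 9 + 18 = 27 active subjects. Assume 4 in LTE (mean 2), 9 in induction-only follow-up (mean 5) and 14 who move to the open-label extension (mean 3.5) and so leave the double-blind series. Week 12 is (8 + 45 + 49)/27 = 3.78, Weeks 16 and 20 are (8 + 45)/13 = 4.08, Week 24 is 2.00 and Week 26 is 5.00.

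**5. Other labels, with the inputs of step 3**

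- *Both tracks share the labels Follow-up 1 to 3.* The series reads 3.67 at Week 12, 2.00 at Weeks 16 to 52 and 3.67 at Follow-up 1 to 3. Follow-up 1 then merges visits 16 − 10 = 6 weeks and 56 − 48 = 8 weeks after the last dose.
- *Each track keeps its own follow-up label.* No visit mixes the tracks. The series still reads 3.67 at Week 12, 2.00 at Weeks 16 to 52, 5.00 at induction-only follow-up and 2.00 at post-LTE follow-up.

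The mean moves under every labelling although nobody changes.

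**6. Split by track.** If each track also shows its own Week 12 value, the two lines are flat at 2.00 and 5.00.

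**7. Outputs reached**

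- Partial Mayo: Tables 14.2-3.3.3 and 14.2-8.7, Figures 15.3.7 and 15.3.15.
- IBDQ: Tables 14.2-3.4.1, .3, .5, .7 and .9.
- Mayo subscores: Tables 14.2-3.9.1, .3 and .5.
- Vital signs: Table 14.3.4-1.1.
- Double-blind hematology, chemistry and urinalysis tables, and Figures 15.4.1, 15.4.3, 15.5.1 and 15.5.3.

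**The case against.** **Labels may already separate the tracks.** SAP 4.1 uses the visit label on the CRF, and SAP 5.1 shows that the Follow-up 3 pages have different names for subjects not entering LTE and for those completing it. Figure 3 is also divided by whether subjects move on. Figure 4, which maps data to summary patterns, was not available in readable form, and the shells are a separate document. This stands in part: a reader might infer that Weeks 16 and 20 certainly average the two tracks, and the documents do not settle that. It does not remove the change of population along one dose-group line.

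**The SAP may exclude these subjects.** SAP 3.4.3 limits the exploratory endpoints to subjects who receive induction and an extension, and the partial Mayo visit list in SAP 7.3 omits Week 26. A reader might therefore infer too readily that a Week 26 spike is planned. Against this, the same section plots all visits, the output titles include the double-blind follow-up, and the IBDQ rule names Week 26. For glucocorticoid dosages SAP 7.3 expressly leaves out subjects who do not move on; no such rule covers these outputs. The text conflicts and needs reconciling.

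**The reach is limited.** A reader might infer that all 16 figures in the 15.4 and 15.5 series are distorted. Eight are open-label, and the four double-blind coagulation and ECG figures have no scheduled follow-up assessments, which leaves four. No vital-sign figure is listed. The mMES, UCEIS, total Mayo and modified Baron outputs leave out follow-up.

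**Partial safeguards exist.** Descriptive tables show n by visit, and subject listings are planned. A falling n hints at a change but does not say which track remains, and SAP 7.3 does not ask for n on the figures.

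**Conclusion.** The point holds as a shortcoming of descriptive outputs. It rests on the pooled follow-up period in footnote 2, the absence of LTE entry as a category in Table 2, the outcome-based LTE entry rule and the differing visit schedules.

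Its size cannot be computed from the documents. A reader might take 3 or 4 points from the illustration as an estimate, but these are assumed gaps. The artefact is zero if the tracks have equal means, which the entry rule makes unlikely. Nor do the documents support calling the induction-only track simply non-responders: qualifying subjects could also decline further treatment.

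The jumps come chiefly from joining visits at which only one track is seen. In a cohort wholly under Amendment 1 with no dropout, Weeks 16 and 20 keep the Week 12 set.

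The primary and secondary endpoints and the proof-of-concept decision use Week 12 data (SAP 4.5), so none of them changes. The MMRM in SAP 7.3 draws on the same combined period but is outside this point.

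**What to change.** 1. In SAP Table 2, split the pattern after Week 12 into (a) LTE with its own follow-up at Weeks 56, 60 and 64, and (b) induction-only follow-up at Weeks 16, 20 and 26.
2. Show (a) and (b) as separate rows and unconnected lines with n per visit, at least for partial Mayo and IBDQ. Give each track its own Week 12 value as a starting point. The subscore, vital-sign and laboratory outputs listed above can follow the same layout.
3. Reconcile SAP 3.4.3 and the partial Mayo visit list in SAP 7.3 with the all-visits plotting rule in SAP 7.3 and the output titles, so that the included subjects and visits are stated once.

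No new data are needed. The cost is SAP and shell wording, a few extra rows or panels, and small numbers per track, given 9 active subjects per Part A dose. The split does not address LTE subjects who flare and move to the open-label extension up to Week 28. They still leave track (a), which is a further reason to show n.
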